8. RESEARCH METHODS

8.1. Study Design

This is a prospective, non-interventional (NI), multicenter study being conducted in Africa Middle East (AfME) countries. The aim is to understand palbociclib treatment patterns, clinical outcomes and QoL for patients with metastatic/locally advanced BC being treated in routine clinical practice in 7 AfME countries: Egypt, Jordan, KSA, Lebanon, Morocco, Qatar and UAE.

Approximately 200 patients from 19 centers across the 7 countries will be enrolled. The recruitment period (ie, from first patient into last patient in) will span over 18 months.

[figure not shown]
Patients will be enrolled at the time of treatment initiation with palbociclib and will be followed up over a 24-month period at time intervals per routine care, or until patient's withdrawal from the study or death (whichever comes first). Prospective data on clinical characteristics, treatment patterns, clinical outcomes and QoL will be collected ([Figure 1](#)).

Participation in this study is not intended to change the routine treatment patients receive, as determined by their prescribing physicians; all treatment decisions, type and timing of the disease monitoring are per routine clinical care, and at the discretion of treating physician and patient.

All assessments described in this protocol are performed as part of normal clinical practice or standard practice guidelines for the patient population and healthcare provider specialty in the countries where this non-interventional study is being conducted.

All assessments described in this protocol are performed as part of normal clinical practice or standard practice guidelines for the patient population and healthcare provider specialty in the countries where this non-interventional study is being conducted.

Figure 1. Study Design

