2. INTRODUCTION

Note: in this document, any text taken directly from the non-interventional (NI) study protocol is ***italicised***. The protocol version 2.0, dated in 13 December 2021 was used to develop the SAP.

Breast cancer (BC) is a complex, heterogenous disease encompassing multiple tumor entities with specific pathologic features and biological behaviors.¹ It is the most common neoplasm among women with an estimated incidence of 2.4 million cases and 523,000 deaths in the year 2015.² Approximately 6%-10% of new BC cases are diagnosed as stage IV metastatic disease and an estimated 20%-30% patients with early BC experience relapse with distant metastatic disease.³

Absolute rates of BC incidence are higher in high-income countries (HICs), however incidence rates are also increasing in lower-middle-income countries (LMICs).² The age-standardized rate (ASR) per 100,000 population for BC worldwide is 43.1.⁴ The highest BC incidence rates are in North America, Australia, New Zealand, and Northern and Western Europe.⁵ The incidence rate varies from 19.4 per 100,000 people in East Africa to 89.7 per 100,000 in West Europe.⁶ Mortality rates of BC depend on the availability of early detection and treatment.⁴ Hence, the mortality rates are higher in many LMICs, such as those in sub-Saharan Africa due to their late stage diagnosis and limited access to treatment as compared to HICs.⁵ The 5 year survival rate is 85% or higher in the United States, Canada, Australia, Israel, Brazil, and many Northern and Western European countries, whereas it is 60% or lower in many LMICs, such as South Africa, Mongolia, Algeria, and India.⁵

Breast cancer is one of the most prevalent cancers in the Middle East (ME), where it is also the most common cause of death among females.⁷ The BC cases diagnosed in this geography are more aggressive and associated with worse outcomes compared to cases evidenced in other parts of the world, which may partly be explained by late diagnosis.⁷

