2.1. Study Design

This is a prospective, non-interventional (NI), multicentre study being conducted in Africa Middle East (AfME) countries. The aim is to understand palbociclib treatment patterns, clinical outcomes and QoL of patients with metastatic/locally advanced BC being treated in routine clinical practice in seven AfME countries: Egypt, Jordan, Lebanon, UAE, Qatar, Morocco and KSA.

Participation in this study is not intended to change the routine treatment patients receive, as determined by their prescribing physicians; all treatment decisions, type and timing of the disease monitoring are per routine clinical care, and at the discretion of the treating physician and patient.

Study population

[figure not shown]
Patients with HR+/HER2- metastatic/locally advanced BC within Egypt, Jordan, Lebanon, UAE, Qatar, Morocco and KSA will be enrolled from a geographically representative population as well as from diverse treatment settings (eg, academic and community sites). Patients whose treatment decision with palbociclib combination has been made by their treating physician and meet the eligibility criteria will be invited to participate in the study in a consecutive manner and over 12 months of recruitment.

Approximately 350-410 patients from 19 centers across the seven countries will be enrolled. The recruitment period (ie, from first patient in to last patient in) will span over 12 months.

Patients will be enrolled at the time of treatment initiation with palbociclib, and will be followed up over a maximum of 24-month period at time intervals per routine care, or until the end of Palbociclib treatment, progression or patients' withdrawal from the study (whichever comes first). Eligibility will be assessed at the date of the enrollment.

Prospective data on clinical characteristics, treatments patterns, clinical outcomes and QoL will be collected in accordance with routine standard of care visits (Figure 1). Data will be collected at enrollment (time of treatment initiation), during treatment with Palbociclib (at time intervals per routine care) and after treatment with palbociclib. After the end of treatment with palbociclib, data related to the first immediate subsequent treatment received will be collected.

Figure 1. Study Design

FPI: first patient in; LPI: last patient in; LPO: last patient out; QoL: quality of life

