2.2.1. Primary Objectives

To determine clinical outcomes including (but not limited to):

- Proportion of patients who are progression free and alive at specific intervals (6, 12, 18 and 24 months). Patients who are not censored (see [Section 3.1](#)) at a certain time point will be included in the analysis.
- Proportion of patients alive after 1 and 2 years post palbociclib combination initiation.

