3. ANALYSIS SETS/POPULATIONS

3.1. Full Analysis Set

The Full Analysis Set will contain all patients who fulfil the eligibility criteria. Date of enrollment is the date of Palbociclib treatment initiation (baseline).

Censoring rules: The maximum follow-up of a patient is 24 months. Patients will be censored at the end of Palbociclib treatment, or if the treatment continues, at 24 months. Other censoring events before 24 months are patient's withdrawal, disease progression or death, whichever occurs first. Patients' subsequent treatments after Palbociclib treatment discontinuation /disease progression will be recorded. Patients who are lost to follow-up will be censored at their last visit. For some clinical outcomes, different censoring rules will be applied as described in [Section 6.1](#), [Section 6.2](#), and [Section 6.3](#).

Data collection is estimated to start in Q2 2021 and it will end in Q4 2024.

Table and Figure Shells are presented in [ANNEX 2](#).

Patient inclusion and exclusion criteria are explained in [Section 2.1](#). Summary of patient enrolment per country and study site will be described as shown in [Table Shell 1](#).

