090177a099673e39a54dc25f1famp15reed On: 28-Mar-2023 09:56 (GMT)

090177a099673e39a54dc25f1famp15reed On: 28-Mar-2023 09:56 (GMT)

090177a099673e39a54dc25f1famp15reed On: 28-Mar-2023 09:56 (GMT)

Table Shell 68 - Descriptive summary table of the first immediate subsequent treatment used following end of treatment with Palbociclib by metastatic site.

Variable	Metastatic site	
	Visceral	Non-visceral
Number of patients who received adjuvant therapies after Palbociclib treatment	XX	XX
Systemic therapy	XX (xx%)	XX (xx%)
Radiotherapy	XX (xx%)	XX (xx%)
Surgery	XX (xx%)	XX (xx%)
Other	XX (xx%)	XX (xx%)
Unknown	XX (xx%)	XX (xx%)
Missing	XX (xx%)	XX (xx%)

Table Shell 69 - Descriptive summary table of the first immediate subsequent treatment used following end of treatment with Palbociclib by age group.

Variable	Age group		
	<55 years	55-64 years	≥65 years
Number of patients who received adjuvant therapies after Palbociclib treatment	XX	XX	XX
Systemic therapy	XX (xx%)	XX (xx%)	XX (xx%)
Radiotherapy	XX (xx%)	XX (xx%)	XX (xx%)
Surgery	XX (xx%)	XX (xx%)	XX (xx%)
Other	XX (xx%)	XX (xx%)	XX (xx%)
Unknown	XX (xx%)	XX (xx%)	XX (xx%)
Missing	XX (xx%)	XX (xx%)	XX (xx%)

Document Approval Record

Document Name:

A5481150_Non Interventional Statistical Analysis Plan_V1_15FEB2022

Document Title:

A5481150_Non Interventional Statistical Analysis Plan_V1_15FEB2022

Signed By:

Date(GMT)

Signing Capacity

PPD

24-Feb-2022 22:47:41

Scientific Review

PPD

28-Feb-2022 10:56:40

Author Approval

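### SAP 2.1 and 3.1 were not updated to protocol version 3.0 (12 v 18 months of recruitment; data end Q4 2024 v 30 April 2025); applying the SAP date would leave about 3% to 19% of patients short of 24 months, which matters mainly for the 2-year-alive proportion

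*SAP*

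**What the plan says.** **SAP.** Section 2 (Introduction) records its basis: "The protocol version 2.0, dated in 13 December 2021 was used to develop the SAP". The approval record at the end of the document names the file "A5481150_Non Interventional Statistical Analysis Plan_V1_15FEB2022", and Section 1 lists no amendments. Section 2.1 states: "The recruitment period (ie, from first patient in to last patient in) will span over 12 months". Section 3.1 states: "Data collection is estimated to start in Q2 2021 and it will end in Q4 2024", and also "The maximum follow-up of a patient is 24 months". Section 2.2.1 lists as a primary objective "Proportion of patients alive after 1 and 2 years post palbociclib combination initiation", and Section 6.1 computes it as a simple ratio over all eligible patients who started treatment. Section 6.1 estimates the progression-free proportion at 6, 12, 18 and 24 months by Kaplan-Meier. Section 5 rules out imputation.

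**Protocol version 3.0 (8 November 2022).** Section 8.1 states: "The recruitment period (ie, from first patient into last patient in) will span over 18 months". It gives 24 months of follow-up per patient and about 200 patients. Section 5 (Milestones) has data collection starting on 15 July 2021 and ending on 30 April 2025, with the final report due on 31 December 2025.

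**The concern.** The SAP is the working document for the analysis. Protocol 8.7 leaves detailed methods to it and allows it to depart from the protocol's outline. The SAP supplied carries a recruitment period and an end of data collection that the protocol has since changed, and it nowhere mentions 30 April 2025. Anyone who takes the data cut from SAP 3.1 would close the data before the last patients reach month 24.

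The two primary outcomes with a 24-month time point are not equally exposed. Kaplan-Meier accommodates patients whose follow-up ends early for calendar reasons. The 2-year-alive ratio does not: a patient cut off alive before month 24 stays in the denominator, and SAP 6.1 does not say how such a patient enters the numerator. If not counted as alive, that patient is in effect treated as dead.

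**Working it through.** **Inputs.** Start of data collection 15 July 2021 and end 30 April 2025 (Protocol 5); recruitment 18 months, follow-up 24 months, N about 200 (Protocol 8.1); recruitment 12 months (SAP 2.1); start Q2 2021, end Q4 2024, follow-up at most 24 months (SAP 3.1). Two assumptions are added: first patient in equals start of data collection, and accrual is uniform.

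**1. The SAP's own timeline.** End = first patient in + recruitment + 24 months.
- Q2 2021 (1 April to 30 June) + 12 + 24 months = 1 April to 30 June 2024. Q4 2024 is not the exact sum, but it covers it, with about six months to spare between 30 June and 31 December 2024.
- Q2 2021 + 18 + 24 months = 1 October to 30 December 2024, still within Q4 2024. The longer recruitment alone does not break the SAP window; the later start is needed as well.

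**2. The protocol's timeline.**
- Last patient in: 15 July 2021 + 18 months = 15 January 2023.
- Last month-24 date: 15 January 2023 + 24 months = 15 January 2025.
- This is 15 days after 31 December 2024, 106 days after 1 October 2024, and 105 days before 30 April 2025.

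**3. Share short of 24 months if the SAP date were applied.** Recruitment lasts 549 days (15 July 2021 to 15 January 2023). Share = days of recruitment later than (close − 24 months) ÷ 549.

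| Data close | Latest enrolment reaching month 24 | Share short | Of 200 | Follow-up of last patient |
|---|---|---|---|---|
| 31 December 2024 | 31 December 2022 | 15/549 = 2.7% | about 5 | about 23.5 months |
| 1 October 2024 | 1 October 2022 | 106/549 = 19.3% | about 39 | about 20.5 months |
| 30 April 2025 (protocol) | 30 April 2023 | 0% | 0 | 24 months |

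**4. Effect on the 2-year-alive proportion.** If every truncated patient were alive at the close but not counted as alive, the ratio would fall by the truncated share: at most 2.7 percentage points for the 31 December close and 19.3 for the 1 October close. Late enrolees who died before the close have a known status and add nothing to this error.

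**The case against.** The strongest reply is that no data are lost under the current protocol. SAP version 1 dates from February 2022, before the November 2022 amendment, and it says which protocol version it follows. Its Q4 2024 statement is a timeline in a passage that begins with an estimate. The censoring rules in SAP 3.1 work patient by patient, and no rule discards data recorded after Q4 2024. The protocol's own end date leaves 105 days after the last month-24 date. In addition, Protocol 7.1 makes the survival objective conditional on how much follow-up is available.

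This stands as far as it goes: truncation happens only if the outdated SAP date is used. It does not remove the conflict between the documents, and it does not tell the analyst how to handle a patient without a known month-24 status in a ratio over all starters.

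A reader might also infer a larger loss by working back from 30 April 2025 to a last patient in on 30 April 2023. The protocol never states that date. It is only the latest enrolment that the end date can accommodate, and with 18 months of recruitment it would put first patient in at about 30 October 2021, not 15 July 2021.

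**Conclusion.** The finding is a version mismatch: SAP 2.1 and 3.1 do not agree with protocol version 3.0 on recruitment length or data-collection dates. Its potential size is about 3% of patients (about 5 of 200) for a close at the end of Q4 2024, rising to about 19% (about 39) only if Q4 is read as its first day. Both figures rest on uniform accrual and on first patient in on 15 July 2021.

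Two stronger readings are not supported. A reader might conclude that late enrolees are cut off as planned; they are not, because the protocol collects data until 30 April 2025. A reader might also conclude that both 24-month primary outcomes would be missing for these patients. The progression-free proportion would be administratively censored within Kaplan-Meier, which is valid if late enrolees resemble earlier ones; the documents say recruitment was difficult, not that late enrolees differ. The real exposure is the crude 2-year-alive ratio.

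**What to change.** - **SAP 3.1:** replace the dates with 15 July 2021 to 30 April 2025, and name 30 April 2025 as the data cut-off.
- **SAP 2.1:** replace 12 with 18 months of recruitment, in both places where it appears.
- **SAP 3.1 and 6.1:** state that a patient whose month 24 falls after the cut-off is administratively censored and not counted as not alive. A simple ratio over all starters has no place for a censored patient, so 6.1 should say how this is done. Kaplan-Meier, which SAP 6 already lists for death, would serve.

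No rule should be added that takes month-24 progression status from visits after month 24. Progression first seen later does not establish status at month 24, and such visits lie outside the 24-month follow-up.

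The cost is SAP wording only. No extra visits, patients or extension of data collection are needed.

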3.2. Subgroups

Exploratory stratifications will be conducted (where adequate numbers of patients permit) to explore differences by eg, country, line of therapy (first or second), menopausal status, age (<55, 55-64, ≥65 years), combination therapy (ie, palbociclib plus letrozole/aromatase inhibitor vs. palbociclib plus fulvestrant), menopausal status, metastatic status (de-novo vs. recurrent disease) and metastatic site (visceral vs. non-visceral). For each stratification variable, the full analysis set will be segmented into non-overlapping subgroups based on the stratification variable values. The stratifications may not be meaningful, if there are no patients in some of the groups or there are many variables with a lot of missing data.

The exploratory stratifications will be conducted for the following study objectives describing the Palbociclib treatment, if enough data are available:

1. *Primary objectives: To determine clinical outcomes, including (but not limited to):*
 - *Proportion of patients who are progression free at multiple intervals (6, 12, 18 and 24 months).*
 - *Proportion of patients alive 1 and 2 years post palbociclib combination initiation - depending on availability of follow-up data.*

2. Secondary objectives:

- Objective response rate (ORR) - depending on availability of follow-up data
- To describe dosing and dose changes, interruptions, delays and discontinuations associated with palbociclib use in clinical practice. To describe supportive therapies received by patients while receiving palbociclib combination treatment.
- To summarize adjuvant therapies received for the treatment of early or locally advanced breast cancer (Stages 0-IIIa).
- To describe treatments received in the advanced/metastatic setting, before and after palbociclib combination use.
- To assess quality of life of patients receiving palbociclib combination treatment.

3. Exploratory objectives:

- To evaluate time to response (TTR), time to progression (TTP)/Progression free survival (PFS) associated with palbociclib combination treatment.
- To describe the first immediate subsequent treatment used following end of treatment with palbociclib.

The specific stratifications, and their corresponding reporting labels will be the following:

- *Combination therapy (ie, palbociclib plus letrozole/aromatase inhibitor, palbociclib plus fulvestrant).* The combination of therapies will be determined at the Palbociclib treatment initiation. Palbociclib plus letrozole/aromatase inhibitor group will be defined as patients receiving Palbociclib and either Anastrozole, Letrozole or Exemastane. Palbociclib plus fulvestrant group will be defined as patients receiving Palbociclib and Fulvestrant. Other endocrine therapies will not be considered in this definition. Descriptive summary tables for the subgroup analysis by combination therapy line for the specified study objectives will be created as shown in [Table Shells 3, 15, 23, 31, 39, 46, 55, 63](#).
- *Line of therapy (1st or 2nd).* Line of therapy will be determined at the Palbociclib treatment initiation and defined as whether Palbociclib has been used as the first or second line endocrine therapy for metastatic/locally advanced BC. Descriptive summary tables for the subgroup analysis by combination therapy line for the specified study objectives will be created as shown in [Table Shells 4, 16, 24, 32, 40, 48, 56, 64](#).

- *Country (Egypt, Jordan, Lebanon, UAE, Qatar, Morocco and KSA).* Descriptive summary tables for subgroup analysis by country for the specified study objectives will be created as shown in Table Shells 5, 17, 25, 33, 41, 49, 57, 65.
- *Menopausal status (premenopausal vs. postmenopausal).* Menopausal status will be assessed at the Palbociclib treatment initiation. Descriptive summary tables for the subgroup analysis by menopausal status for the specified study objectives will be created as shown in Table Shells 6, 18, 26, 34, 42, 50, 58, 66.
- *Metastatic status (de novo vs. recurrent disease)* The recurrence of the disease will be assessed at the Palbociclib treatment initiation. Descriptive summary tables for the subgroup analysis by disease recurrence for the specified study objectives will be created as shown in Table Shells 7, 19, 27, 35, 43, 51, 59, 67.
- *Metastatic site (visceral vs. non-visceral).* Visceral metastases refers to lung, liver, brain, pleural, and peritoneal involvement. Metastatic site will be defined according to the baseline lesion data. Visceral metastases will refer to lung, liver, brain, pleural, and peritoneal involvement. Non-visceral metastases include lesions in bone and skin/soft tissues. Lesions in lymph nodes will be categorised to neither of the groups. Lesions in bone may also be categorised to bone-only category. Descriptive summary tables will be presented as shown in Table Shells 8, 20, 28, 36, 44, 52, 60, 68.
- *Age (<55, 55-64, ≥65).* The age of the patient will be determined at the Palbociclib treatment initiation. Descriptive summary tables for the subgroup analysis by age for the specified study objectives will be created as shown in Table Shells 9, 21, 29, 37, 45, 53, 61, 69.

Additional stratifications can be conducted by eg, ECOG performance (stratified into groups 0-5), endocrine sensitivity vs. endocrine resistance (primary and secondary), if relevant and/or enough data are available.

